3.2.2. Epworth Sleepiness Scale (ESS) Total Score

The ESS scale is used to determine the level of daytime sleepiness. There are 8 situations listed for which patients rate their likelihood of dozing or sleeping (0=would never nod off, 1=slight chance of nodding off, 2=moderate chance of nodding off, or 3=high chance of nodding off). The total score is the sum of 8 item scores and can range between 0 and 24. The higher total score indicates the higher level of daytime sleepiness. A score of 10 or more is considered sleepy, and a score of 18 or more is very sleepy.

In case of missing item scores from the ESS, the missing value will be replaced by the average of non-missing scores at the same visit from the same subject. In case all item scores are missing, the total score will be set as missing.

3.2.3. Adverse Event (AE)

An AE is defined as any untoward medical occurrence in a patient or clinical trial subject, temporally associated with the use of trial intervention, whether considered related to the trial intervention. NOTE: Signs and symptoms and/or abnormal laboratory test result indicating a common underlying pathology/diagnosis should be reported as a single AE.

All adverse events will be recorded on the ADVERSE EVENTS eCRF. Adverse events with missing severity will have the severity imputed as 'Severe' for the AE tabulations. Adverse events with missing relationship to IMP will have the relationship imputed as 'Related' for the AE tabulations if the AE started on or after the first dose of IMP. However, in the data listings these missing intensity severity and/or relationship will be presented as missing.

3.2.3.1. Adverse Event of Special Interest (AESI)

For this study, any AEs related to abuse potential, abnormal liver function tests with a value $>3 \times$ ULN for ALT or AST and $>2 \times$ ULN for total bilirubin within the same visit, a value of $>3 \times$ ULN for ALT or AST and clinical jaundice, an AE leading to the discontinuation of IMP or from the study will be considered AESIs. These events will be noted by the investigator in the ADVERSE EVENTS eCRF

3.2.3.2. Treatment-emergent Adverse Event (TEAE)

Any event reported on the eCRF that occurs on or after the initiation of IMP until the end of AE reporting period per protocol is considered treatment emergent. Additionally, it is assumed that an Adverse Event which was reported to have started on Day 1 without an associated onset time is assumed to be treatment emergent.

3.2.4. Clinical Safety Laboratory Assessments

The clinical laboratory tests as listed in the protocol will be performed in accordance with the laboratory manual and the Schedule of Assessments. All results, including repeats, will be included in the laboratory reports. The investigator must review the laboratory report, document this review, and record any clinically relevant changes occurring during the trial in the AE section of the eCRF.

3.2.4.1. Treatment-emergent Laboratory Abnormality and Toxicity

A treatment-emergent laboratory abnormality is defined as value outside the normal range which occurs on or after the start of IMP and up to 28 days following discontinuation of IMP.

A treatment-emergent laboratory toxicity is defined as an increase of at least one CTCAE toxicity grade (Version 5) from the baseline assessment at any post baseline visit which occurs after the first administration of IMP and through last test results of the study. If a laboratory assessment obtained on Day 1 with unknown collection times will be assumed to be an assessment prior to the initiation of IMP. If the relevant baseline assessments are missing for a given subject, then any post-baseline graded toxicity (i.e., at least Grade 1) is considered a treatment-emergent laboratory toxicity.

3.2.5. Columbia-Suicide Severity Rating Scale (C-SSRS)

Suicidality will be monitored during the trial using the C-SSRS. It was designed to quantify the severity of suicidal ideation and behavior.

This trial will use the “Baseline/Screening” and “Since Last Visit” versions of the scale. The “Baseline/Screening” version, which assesses the lifetime experience of the subject with suicide events and suicidal ideation and the occurrence of suicide events or ideation within a specified time period prior to entry into the trial, will be completed for all subjects at screening to determine eligibility and confirmed at baseline. Any subject with active suicidal ideation or suicidal behaviors within the last 6 months, suicidal behaviors within the last 2 years, or who in the clinical judgment of the investigator presents a serious risk of suicide should be excluded from the trial.

The “Since Last Visit” C-SSRS form will be completed at all visits after screening and baseline. The investigator will review the results of the “Since Last Visit” C-SSRS during the trial to determine whether it is safe for the subject to continue in the trial. If a subject demonstrates potential suicidal ideation associated with actual intent or method or plan as indicated by “YES” answers on item 4 or 5 of the C-SSRS, the investigator will evaluate whether a risk assessment by a qualified mental health professional (or the investigator alone if the investigator is a qualified mental health professional) is needed and whether the subject should continue in or be discontinued from the trial.

Details of C-SSR categories as well as definition of treatment emerging events are provided in [Section 9.4](#).

3.2.6. Vital Signs

Vital signs include systolic and diastolic blood pressures, heart rate, and body temperature. Duplicate measurements of blood pressure and heart rate will be obtained supine (after 5 minutes of rest) and 1 measurement of blood pressure and heart rate will be obtained on standing (2 minutes after rising from supine to standing). The duplicate values will be individually recorded, and the values will be averaged by the sponsor for the time point assessment. Body temperature will be obtained once, at the time of the first blood pressure measurement.

3.2.7. Electrocardiograms

Single or triplicate 12 lead ECGs will be obtained during the trial. All ECG recordings be obtained after the subject has been supine and at rest for at least 5 minutes. A triplicate set of ECGs is 3 consecutive ECGs collected 1 to 2 minutes apart over a 5 minute period.

A single ECG will be obtained at the Screening Visit. One set of triplicate ECGs will be obtained before administration of the first dose of IMP on Day 1, and a single ECG will be obtained ~1 hour after administration of the first dose of IMP, just prior to the time of collection of the PK blood sample on Day 1. Single ECGs will be obtained at the Weeks 5, 11, 14, 22, and 27 clinic visits, just prior to the time of collection of the PK blood sample. A central ECG service will be used for reading all ECGs to standardize interpretations for the safety analysis.

3.2.8. Concomitant Medications and Medications Taken Post Last Dose of IMP

Concomitant medications are those medications taken on or after the initiation of IMP. These medications include those medications started before the initiation of IMP and continuing post Day 1. Medications that start after the last dose of IMP until the end of protocol-specified reporting period will be classified as taken post last dose and will not be considered concomitant. These medications will be recorded in the eCRF. The investigator will record all medications and therapies (including vaccines, over-the-counter or prescription medicines, vitamins, and/or herbal supplements) that are used by the subject from 30 days before the informed consent form (ICF) is signed through the end of the 4-week Safety Follow-up Period (Week 31 or early termination). The investigator will also record all medications and therapies taken or received by a subject for treatment of an AE or that cause an AE through Week 31 or early termination.

3.2.9. Physical and Neurological Examinations

A complete physical and neurological examinations will be conducted at screening and at the end of treatment visit (Visit 11 or early termination visit). Any condition present post-baseline physical or neurological examination that was not present at the baseline examination should be documented as an AE and followed to a satisfactory conclusion.

3.3. Pharmacokinetics

Blood samples for measurement of plasma concentrations of tavapadon and CVL-0000053, its major metabolite, will be collected ~1 hour after administration of the first dose of IMP on Day 1 and at the clinic visits at the end of Weeks 5, 11, 14, 22, and 27.

Drug concentration information will not be reported to investigative sites, clinical database or any blinded study personnel until the trial has been completed and unblinded.

4. DATA CONVENTIONS AND VISIT WINDOWS

4.1. Data Conventions

4.1.1. Age

Age is the age at the time of informed consent and is as captured on the eCRF (note: date of birth is not captured on the eCRF).

4.1.2. Day 1

Day 1 is the day IMP is first initiated.

4.1.3. Endpoint

Endpoint as defined as the primary time point for the efficacy assessments is Week 26.

4.1.4. Study Day of an Event

Study day of an event is defined relative to Day 1 as:

Study Day = event date – date of Day 1 (+ 1, if event date \geq date of Day 1).

This calculation will result in negative study days for an event occurring prior to the start of IMP and positive study days for an event on or after the start of IMP. There will be no Day 0 value to match the schedule of events.

4.1.5. Days on Study

Days on Study is the number of days from Day 1 to the date of study completion or early termination as recorded on the END OF STUDY eCRF.

4.1.6. Days on IMP

Days on IMP is the number of days from Day 1 to the date of last dose of IMP as recorded on the EXPOSURE eCRF.

4.1.7. Baseline Value

For purposes of analysis, the baseline value of a given assessment is defined as the last value obtained prior to initiation of IMP. Should the Day 1 visit value be obtained after the first dose of IMP or if this value is not available at Day 1, the most recent value obtained prior to the first dose of IMP will be used for the baseline value.

For ECGs, baseline is defined as the average of the triplicates at predose timepoint prior to the IMP administration. If the predose triplicate is not available, the average of the triplicates at the last visit prior to the IMP administration will be used (scheduled records will be selected over unscheduled records if both are present). If no triplicate is available, the last non-missing value prior to the initiation of IMP will be used.

For blood pressure and heart rate measurements, baseline is defined as the average of the duplicates at the last visit prior to the IMP administration. If no duplicate is available, the last non-missing value prior to the initiation of IMP will be used.

4.1.8. Change from Baseline

Change from baseline for a given variable is defined as the value on a given Study Day (Time Point) minus the Baseline Value.

4.1.9. Orthostatic Change

Orthostatic change is calculated as the difference in the standing value from the supine value (i.e., supine value – standing value). If an average value is available at a given visit and date, it will be used for the calculation of orthostatic change. If an average value is not available, the individual record obtained on a given visit and date will be used.

4.1.10. Duration of Titration Phase

The duration of the titration phase will be calculated as the days in [REDACTED] of the dosing schedule.

4.1.11. Duration of Adjustment Phase

The duration of the adjustment phase will be calculated as the days in [REDACTED] of the dosing schedule.

4.1.12. Duration of Maintenance Phase

The duration of the maintenance phase will be calculated as the days in [REDACTED] of the dosing schedule.

4.1.13. Average Dose of Titration Phase

The average dose of the titration phase will be calculated as the sum of the milligrams of study drug taken in [REDACTED] of the dosing schedule divided by the duration of days in the titration phase.

4.1.14. Average Dose of Adjustment Phase

The average dose of the adjustment phase will be calculated as the sum of the milligrams of study drug taken in [REDACTED] of the dosing schedule divided by the duration of days in the adjustment phase.

4.1.15. Average Dose of Maintenance Phase

The average dose of the maintenance phase will be calculated as the sum of the milligrams of study drug taken in [REDACTED] of the dosing schedule divided by the duration of days in the maintenance phase.

4.1.16. Average Dose of L-Dopa

The average dose of L-Dopa is calculated as the sum of the milligrams of L-Dopa taken from the time of informed consent to the date of study completion or early termination divided by the number of days on study. Records with a dosing frequency that is unknown or as needed will be excluded from the calculation.

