9.	Subjects who are on a stable dose of L-Dopa for at least 4 weeks prior to screening and are taking a minimum total daily dose of 400 mg divided in at least 4 doses per day of standard carbidopa/levodopa or divided in at least 3 doses per day of extended-release carbidopa/levodopa capsules. The carbidopa/levodopa dose and frequency must be maintained for the duration of the trial. Standard or extended-release levodopa/benserazide is allowed as an alternative to levodopa/carbidopa, where available. The minimum dose and frequency requirements for levodopa still apply.
10.	Prior and concurrent use of COMT inhibitors, MAO-B inhibitors, amantadine, istradefylline, or anticholinergic drugs is permitted if use was initiated >90 days before the Baseline Visit and the dosage will remain stable for the duration of the trial (ie, no change in the COMT, MAO-B inhibitor, amantadine, istradefylline, or anticholinergic dose is permitted during the trial).

Abbreviations: COMT = catechol-O-methyl transferase, ICF = informed consent form, IMP = investigational medicinal product, L-Dopa = levodopa, MAO-B = monoamine oxidase inhibitor B, PD = Parkinson's disease.

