1.1. Study Overview

This is a prospective, Phase 3, multicenter, multinational, randomized, double blind, placebo controlled, parallel group, 27 week trial to evaluate the efficacy, safety, tolerability, and pharmacokinetics (PK) of flexible doses of tavapadon (5 mg to 15 mg once daily [QD]) as adjunctive therapy to levodopa (L Dopa) in male and female subjects aged 40 to 80 years who have a diagnosis of PD (consistent with the UK Parkinson's Disease Society Brain Bank diagnostic criteria); a modified Hoehn and Yahr score of 2, 2.5, or 3 in the "on" state; a minimum of 2½ hours of "off" time on 2 consecutive days; and a good response to L Dopa in the judgment of the investigator. The trial will include a Screening Period (maximum of 4 weeks), a 27 week Treatment Period, and a 4 week Safety Follow up Period. Details of schedule of assessments are provided in [Section 9.2](#).

A total of 368 subjects are planned to be randomized in a 1:1 ratio to receive tavapadon or placebo once daily (184 subjects per treatment group). The dose of tavapadon will be titrated and adjusted over the first 13 weeks of the trial and then maintained for 14 weeks. The planned duration of treatment is 27 weeks, including the Titration and Maintenance Phases. The investigational medicinal products (IMPs) will be taken orally.

The trial design is depicted in [Figure 1](#).

Figure 1: Trial Schematic

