Subjects will receive the highest tolerated dose level that is achieved during the Dose Adjustment Phase for the duration of the subsequent 13-week Maintenance Phase. Adjustments in the dose of tavapadon will not be allowed during the Maintenance Phase. Subjects who cannot tolerate their maintenance dose will be discontinued from the trial. Subjects will be considered to have completed this trial once they complete the assessments that are scheduled at the Week 27 visit.

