5.6. Subject Disposition, Demographic and Baseline Characteristics

Subject disposition will be based on the ITT population with tabulation of the number of subjects who complete the study and the number of discontinued and from the study and the reasons by treatment group. Additionally, the number of days on study will be summarized.

Tabulation of subject randomization by country and site will be presented for the ITT population and for completed subjects. A listing of randomization number, subject, treatment randomized, country, and site will be provided. Further tabulation by region (United States, Non-US) and country will also be presented. Subject disposition data will also be tabulated for all subjects screened to include the number of subjects screened, the number of screen failures, and the reason for screen failure.

Kaplan-Meier (KM) plots will be used to assess time to discontinuation of study, time to discontinuation of study due to adverse events, and time to discontinuation of study due to subject withdrawal. The complete subjects will be censored at the time of end of study for the KM analyses.

Number of subjects in each analysis population set will be summarized.

Demographic data and baseline characteristics including age, age categorical distribution, gender, childbearing potential, race, ethnicity, height at screening, weight at screening and baseline, BMI at screening and baseline, history of Parkinson's disease (including years from initial diagnosis), baseline on time without troublesome dyskinesia, baseline off time, Montreal Cognitive Assessment (MoCA) total score, Modified Hoehn & Yahr assessment at screening, MDS-UPDRS score at baseline, and L-dopa dose at baseline will be summarized using descriptive statistics for the ITT population. Use of PD medications (ATC classifications of ADAMANTANE DERIVATIVES, OTHER DOPAMINERGIC AGENTS, OTHER ANTIPARKINSON DRUGS, MONOAMINE OXIDASE B INHIBITORS, or ANTICHOLINESTERASES) at baseline will also be summarized. Further tabulation by region and country will also be presented.

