5.8. Exposure to Treatment

The number of days on study drug, reasons for premature discontinuation of IMP, treatment compliance, days in each phase (Titration, Adjustment, and Maintenance), average dose in each phase, average L-Dopa dose during treatment period, and maximum tolerated dose will be summarized by treatment group for the FAS Population.

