5.15.4. Non-IMP Medications and Non-Drug Therapy/Procedures

The use of non-IMP medications will be coded using the World Health Organization (WHO) drug dictionary (WHODrug) ([Version: Global B3 September 2019 or later](#)). Concomitant medications, with start date on or after the date of the first IMP through the last IMP dose date, will be summarized by treatment group, frequency of drug classification, and generic drug name. Incidence of dosage adjustment of levodopa (L-Dopa) or equivalent during treatment period, prohibited by the protocol, for duration longer than one week will be summarized. Medications with start date after the last dose of IMP through the end of protocol-defined reporting period, will also be summarized. All prior, concomitant, and post IMP medications will be presented in a data listing.

The use of non-drug therapy/procedures will be coded using MedDRA Version 26.1 or higher. Concomitant and post-IMP non-drug therapy/procedures will be summarized by treatment group, frequency of system organ class and preferred term. All prior, concomitant, and post-IMP non-drug therapy/procedures will be presented in a data listing.

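### The average L-Dopa dose in SAP 4.1.16 counts milligrams from informed consent but divides by days from Day 1, so it overstates the daily dose even when the dose never changes

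*SAP*

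**What the plan says.** SAP 4.1.16 defines the numerator as "the sum of the milligrams of L-Dopa taken from the time of informed consent to the date of study completion or early termination" and divides it by the number of days on study. Records with unknown or as-needed dosing frequency are left out.

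SAP 4.1.5 fixes the denominator: "Days on Study is the number of days from Day 1 to the date of study completion or early termination". SAP 4.1.2 makes Day 1 the day of the first IMP dose.

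SAP 5.8 then lists the result for the FAS, by treatment group, as the "average L-Dopa dose during treatment period".

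Two other outputs concern L-Dopa. In SAP 5.6, "L-dopa dose at baseline will be summarized using descriptive statistics for the ITT population". SAP 5.15.4 summarises, for changes lasting more than one week, the "Incidence of dosage adjustment of levodopa (L-Dopa) or equivalent during treatment period, prohibited by the protocol".

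**The concern.** The two parts of the ratio cover different periods. The numerator begins at consent and so takes in screening, whereas the denominator begins at the first IMP dose. Screening L-Dopa is real and recorded: Protocol 5.1 (inclusion criterion 9) requires a stable dose for at least 4 weeks before screening, and SAP 3.2.8 collects medications from 30 days before consent. The exclusion of as-needed and unknown-frequency records does not touch the mismatch.

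Protocol 6.5.2 forbids any change in L-Dopa dose or frequency, so a natural use of this summary is to show that background therapy held steady. As written, a trial in which nobody changed dose would report an on-treatment average above the baseline dose in both arms. That would look like a prohibited increase and would sit badly beside the adjustment summary in SAP 5.15.4. Because the error grows as follow-up shortens, unequal dropout between arms would also add a small false difference between them.

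**Working it through.** The documents give no numerical value for this average, so there is no stated figure to reproduce. The check is direct arithmetic.

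**Inputs from the documents**
- Screening length, maximum: 28 days. SAP 1.1: "The trial will include a Screening Period (maximum of 4 weeks" and so on. The schedule in SAP 9.2 allows Day -31 to Day -1, which is 31 days.
- Days on study for a completer: 189. SAP 1.4: "Subjects will be considered to have completed this trial once they complete the assessments that are scheduled at the Week 27 visit". SAP 9.2 sets that visit at Day 189 ± 3.
- Minimum L-Dopa dose: Protocol 5.1 requires subjects to be "taking a minimum total daily dose of 400 mg".
- Dropout: 27% overall (SAP 1.2), with no split by arm and no timing.

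**Assumed inputs:** a 7-day screening as a short case, a 600 mg/day dose, and the dropout split and exit days in the last step.

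**Formula.** With constant daily dose D, s days from consent to the day before Day 1, and t days on study:

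- average under 4.1.16 = D × (s + t) / t
- relative inflation = s / t
- average with matched windows = D × t / t = D, so zero inflation

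**Completers, t = 189**
- s = 7: 7/189 = 3.7%
- s = 28: 28/189 = 14.8% (28/192 = 14.6% to 28/186 = 15.1% across the visit window)
- s = 31: 31/189 = 16.4%

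**In milligrams, s = 28, t = 189**
- 400 × 217/189 = 459.3 mg/day instead of 400
- 600 × 217/189 = 688.9 mg/day instead of 600

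**Early leavers, s = 28**
- t = 98: 28/98 = 28.6%
- t = 35: 28/35 = 80.0%
- t = 28: 28/28 = 100%

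The reported value at least doubles whenever days on study do not exceed screening days.

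**False difference between arms (illustration only).** If dropout proportions are d1 and d0, all dropouts leave on day t, and dose and screening length are the same in both arms, the false difference is (d1 − d0) × D × (s/t − s/189). With an assumed 29% versus 25%, D = 600 and s = 28, the multiplier is 0.04 × 600 = 24:
- t = 30: 24 × (0.933 − 0.148) = 18.8 mg/day
- t = 60: 24 × (0.467 − 0.148) = 7.6 mg/day
- t = 98: 24 × (0.286 − 0.148) = 3.3 mg/day
- equal dropout rate and timing: 0

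**The case against.** The best defence of the text is that 4.1.16 names its own window and that lower-case days on study simply means the days in that window. A constant dose would then give no inflation. This does not survive the rest of the SAP. Section 4.1.5 defines the term from Day 1, and 4.1.18 uses the same lower-case phrase to work out expected IMP tablets, which makes sense only from Day 1. Even if the reading were granted, the average would include screening and would still not be the treatment-period figure that 5.8 names.

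The objections to the size of the consequence have more force, and these points stand:
- No planned output compares baseline with on-treatment L-Dopa. The baseline dose is on the ITT population and the average on the FAS, so a reader must put two tables together to see an apparent increase.
- An inflated mean does not strictly contradict the incidence summary in 5.15.4. That summary is the direct check on dose stability and is unaffected.
- With similar screening length and dropout in the two arms, the inflation is similar in both and largely cancels in a comparison.
- The documents give no typical screening length; 14.8% belongs to a completer with the full 4 weeks.
- The arm-difference figures rest on assumed inputs and are small: 3.3 to 18.8 mg/day is about 0.5% to 3.1% of 600.

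These limit the importance of the error. They do not make the formula right.

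**Conclusion.** The concern holds. Followed exactly, SAP 4.1.16 returns a value above the true daily dose for every subject with a screening interval who takes a constant dose. No other section corrects it. For completers the overstatement is about 4% to 16% for screening of 7 (assumed) to 31 days, and 14.8% at the 4-week maximum; it rises steeply for early leavers. These figures rest on a constant dose, as the protocol requires, and on completion at the Week 27 visit. If the end-of-study date were instead the Week 31 contact (an assumption), the 28-day case would be 28/217 = 12.9%.

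The error affects one descriptive exposure line. The estimands, the MMRM, the subgroup analyses and the alpha do not use this variable. It should be corrected, but it does not threaten the trial's conclusions.

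**What to change.** In SAP 4.1.16, start the numerator at Day 1: total L-Dopa milligrams from Day 1 to study completion or early termination, divided by Days on Study. If 5.8 is meant strictly as the treatment period, use milligrams from Day 1 to the last IMP dose divided by Days on IMP (SAP 4.1.6). Either choice follows the approach of 4.1.13 to 4.1.15, where the milligrams taken in a phase are divided by the days in that phase. If an average before Day 1 is wanted, report it separately.

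The cost is one phrase in the SAP and the matching line of programming. It needs no new data and changes no efficacy analysis or clinical rule.
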